3. **Sleep interaction:** To characterize the degree to which sleep mediates the effect of suvorexant on drug cue reactivity. We hypothesize an indirect effect of suvorexant on drug cue reactivity via sleep, such that attenuation of cocaine cue reactivity (attentional bias, craving) will be greater in those with larger improvements in sleep duration.

*Conceptual Model:
Orexin System Effects on Relapse Risk*

Figure 1. Summary of Conceptual Model

Research Plan

Our group at the University of Texas Center for Neurobehavioral Research on Addiction (CNRA) has developed, utilized, and validated laboratory models of drug relapse, allowing us to examine pharmacotherapeutic and cognitive-behavioral interventions for relapse prevention.

Study design. To accomplish the project aims, we will utilize a mixed-model experimental design, with a between-groups factor of dose (suvorexant vs. placebo) and a within-subjects factor of time. Subjects will receive suvorexant (**10 mg week 1, 20 mg week 2**) or placebo PO, once daily at 10 PM. Medication condition will be double-blind, with urn-randomized assignment to dose condition balanced by gender and severity of cocaine use. A summary of timelines and measures is shown in the Table below.

Mon	Wed	Fri	Mon	Wed	Fri	Mon
1,4,5,6,7	1,2,3,4,5	1,2,3,4,5	1,2,3,4,5,6,7	1,2,3,4,5	1,2,3,4,5	1,2,3,4,5,6,7
Key: (1) Provide medication (MEMS bottle); (2) Compliance data for medication adherence (MEMS, pill count, riboflavin, text message); (3) Side effects data, med check, UA toxicology; (4) Sleep data; (5) stress /anxiety data; (6) acute stressor challenge (cold pressor); (7) Cue reactivity data						

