Participants and setting. The study will test 30 current cocaine users (enroll 45 to complete 30), 19 to 55 years old, who meet current DSM-5 criteria for cocaine use disorder (CUD) of at least moderate severity (≥ 4 symptoms). Subjects meeting criteria for substance use disorders other than cocaine, marijuana, or nicotine will be excluded. Notably, because the study medication (suvorexant) is contraindicated with alcohol use, we will exclude subjects with alcohol use disorders (via screening at intake). We will also exclude those individuals who are drinking > 10 alcoholic drinks per week (NIAAA criteria problem drinking = at least 14 drinks per week), and who are unwilling to stop using alcohol in the evening for the two weeks of the study. We will exclude those who report binge drinking (NIAAA criteria = in < 2.5 hours, 5 drinks for men, 4 drinks for women).

Other exclusion criteria will include significant and unstable medical/ psychiatric disorders which might make participation hazardous; acute or chronic health conditions; and concomitant medication use contraindicated with the study medication (suvorexant). This will be accomplished via full medical evaluation at intake by [name], M.D., CNRA Medical Director. The study will be conducted at the Neurobehavioral Research Laboratory at the CNRA, directed by [name]. Recruitment strategies will include local advertising in print media, public service announcements on radio, and referrals to CNRA in the Houston metropolitan area. Based on previous and current CNRA recruitment rates of participants with CUD, we expect to enroll 3-4 participants per month to meet recruitment goals.

Measurements

Cue reactivity: Attention bias (AB) task is a saccade-based eye-tracking measurement, developed by [name] to assess attentional bias to drug cues⁴⁸. Eye movements (saccades) have advantages over other variables because they are directly observable, ecologically valid, and typically stable across repeated measures^{49,50}. AB measures utilizing eye movements have produced moderate to robust effects for a broad class abused substances⁵¹⁻⁵³, including cocaine^{34,48,54}. Using our drug specific anti-saccade task, the between-group effect size for anti-saccade error rates in the presence of cocaine cues was large: CUD vs. control Cohen's $d_{av} = 0.6$ ⁴⁸.

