Data Analyses. We will use multilevel modeling to evaluate cue reactivity (attentional bias, craving) as a function of suvorexant, time, and the interaction of suvorexant x time. Hypothesis evaluation will utilize both Frequentist and Bayesian methods. Power and sample size focus on the effect of suvorexant on drug cue reactivity (AB, CCQ). From a Frequentist perspective, assuming a correlation of $r = 0.5$ between measurement points and $\alpha = 0.05$, a sample of $N=30$ participants will provide 80% power to detect a moderate effect (Cohen’s $f = .0.24$) for the interaction if treatment and time. For Bayesian analyses, multilevel priors will be vague and neutral: coefficients ~Normal (mean = 0, variance = 1×10^6), level 1 variance ~ Gamma (shape=.001, scale=.001), level 2 variances ~ Uniform (0,100). Frequentist statistical models will utilize traditional mediation analyses as recommended by Baron and Kenny⁶⁸, which permits unbiased OLS estimates appropriate for this experimental design and sample size⁶⁹, and which we have utilized in previous published research⁷⁰. Bayesian statistical models will utilize path analysis (BSEM) to evaluate the mediating effects of stress/anxiety (biological and subjective-rated) and sleep (biological and subject-rated) for the effects of suvorexant on drug cue reactivity. An example of a mediation analysis using Bayesian SEM may be found Arbuckle⁷¹. Uncertainty surrounding the Bayesian estimate for the indirect effect employs the posterior distribution of the parameter (i.e. the product coefficient): a density denoting the probability that different values of the parameter obtain given the observed data. This approach may be particularly important for evaluating more complex mediation models (e.g. multiple mediators, latent variables) in the context of small sample sizes. Use of the MCMC (Monte Carlo Markov Chain) approach in Bayesian analyses has demonstrated superior small sample performance relative to maximum likelihood-based approaches in continuous, normally distributed data⁷². These properties are likely due to the MCMC approach’s lack of reliance on large sample size assumptions⁷³. BSEM prior specification will adapt recommendations from Muthén and Asparouhov⁷⁴.

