Demographic characteristics of cocaine-dependent patients recruited into treatment studies show a mean age of 41 years, 83% are male, 15% Caucasian, 75% African-American, 10% Hispanic. Men and women of all ethnic backgrounds will be recruited to participate. It is anticipated that the subject demographic profile will closely mirror the larger population from which they are recruited, however, because we are recruiting non-treatment seekers, we expect to a broader range of subjects to select from and anticipate a 70% / 30% male/female subject distribution. Efforts will be made to increase the percentage of women in the study. These efforts will include (1) having the outreach coordinator present educational material and referral information at women's clinics in the greater Houston area.

Children (defined here per NIH guidelines as 19-21 years old) will be included in this research. The incidence of severe cocaine use disorder is relatively small in the population of youth less than 18 years old. From a safety perspective, risks of exposure to the proposed study medication in substance dependent children have not been established. The safety and efficacy of the proposed study medication should be established in adults first, before conducting this type of treatment research in children.

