Research participation may assist non-treatment seeking subjects in abstaining from cocaine during study, and via study completion protocol, bring them into contact with treatment resources at our research center and in the community. Cocaine dependence is marked by repeated relapse, leading to devastating consequences on a personal and societal level. Currently, there is no medication that has been shown to be broadly effective in reducing cocaine use. Suvorexant (and orexin agonists more broadly), may help reduce sleep disruptions and anxiety, and attenuate craving and biased attention toward drug cues – helping to reduce risk of relapse. This experiment will compliment and provide valuable information to our ongoing and future addiction work, and contribute to the knowledge base in the treatment of cocaine dependence. Our procedures have been designed to minimize the probability of risks. Our research center has an excellent track record in conducting human psychopharmacology experiments and clinical trials with the utmost attention to safety.

E7. Inclusion of Women and Minorities

Women, minorities, and children will be included at minimum to the extent they are reflected in this cocaine-dependent population. In previous cocaine clinical studies at the Treatment Research Clinic (TRC), the percentage of females and males is approximately 20% and 80% respectively. We will continue recruitment efforts to achieve a 50-50 balance and thus permit meaningful analyses by sex across groups. One effort will be to have the TRC outreach coordinator present educational material and referral information at women's clinics in Houston and the surrounding communities. In the past this has helped to enhance recruitment of women with cocaine dependence.

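### Thirty completers in two arms cannot support informative analyses by sex, even if the 50-50 recruitment target in E7 is met

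*Combined protocol and SAP*

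**What the plan says.** Section E7 (Inclusion of Women and Minorities) reports past experience at the clinic, where "the percentage of females and males is approximately 20% and 80% respectively", and then sets an aim: "We will continue recruitment efforts to achieve a 50-50 balance and thus permit meaningful analyses by sex across groups". Section E1 gives the forecast for this study. Because non-treatment seekers are recruited, the investigators "anticipate a 70% / 30% male/female subject distribution", and they add that they will try to raise the share of women.

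On size, Participants and setting states: "The study will test 30 current cocaine users (enroll 45 to complete 30". Study design describes "a between-groups factor of dose (suvorexant vs. placebo) and a within-subjects factor of time", with "urn-randomized assignment to dose condition balanced by gender and severity of cocaine use". The allocation ratio is not stated.

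Data Analyses models cue reactivity on suvorexant, time and their interaction, and sizes the trial for that interaction only: 30 "participants will provide 80% power to detect a moderate effect". It contains no sex term, no sex subgroup, no sex interaction and no power figure for one. The three specific aims do not mention sex either.

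**The concern.** The E7 sentence treats balance as sufficient: reach 50-50, and analyses by sex follow. But the precision of an effect within women depends on how many women there are in each arm, and the precision of a sex difference depends on all four sex-by-arm cells. Balance makes the best use of a given total; it does not make a small total large. With 30 completers, perfect balance leaves 7 to 8 people per sex per arm.

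A by-sex result from this trial would be one that the analysis plan neither defines nor sizes, yet E7 could be cited in support of it. An apparent effect in one sex, or a non-significant difference between the sexes, would then carry more weight than the data can bear.

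**Working it through.** **Inputs.** N = 30 completers (Participants and setting; E1). Two arms (Study design). Effect f = 0.24 for treatment by time, correlation r = 0.5 between measurements, alpha 0.05 (Data Analyses; the effect is printed with a stray decimal point and is read here as 0.24). Cue reactivity is measured m = 3 times, on days 1, 7 and 14 (Subject participation requirements). Share of women: 50% as target (E7), 30% as forecast (E1), 20% as history (E7). Assumed, because the protocol does not say: 1:1 allocation, and equal completion in men and women.

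**Step 1: reproduce the protocol's figure.** For the treatment-by-time interaction with g = 2 groups, use the noncentral F distribution with

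λ = N·m·f²/(1 − r), df1 = (g − 1)(m − 1), df2 = (N − g)(m − 1).

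λ = 30 × 3 × 0.0576 / 0.5 = 10.37, df1 = 2, df2 = 56. Power is 80.8%, and the effect detectable at 80% power is f = 0.238. The stated 80% is reproduced. With two visits instead of three the same formula gives 71.8%, so three visits is the basis that fits.

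**Step 2: count the women.** 30 × 0.50 = 15 (7 to 8 per arm); 30 × 0.30 = 9 (4 to 5 per arm); 30 × 0.20 = 6 (3 per arm). Because the urn balances on gender, women should divide about evenly between arms.

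**Step 3: power for the planned effect within one sex.** Same formula, with N set to the number in that sex.

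| Subgroup | n | λ | df2 | Power at f = 0.24 | f detectable at 80% power |
|---|---|---|---|---|---|
| Women (or men) at 50-50 | 15 | 5.18 | 26 | 47% | 0.35 |
| Women at 70/30 | 9 | 3.11 | 14 | 27% | 0.47 |
| Women at 80/20 | 6 | 2.07 | 8 | 17% | 0.63 |
| Men at 70/30 | 21 | 7.26 | 38 | 64% | 0.29 |

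**Step 4: power for a difference between the sexes.** Suppose the treatment-by-time effect differs between men and women by as much as the whole planned effect, for instance fully present in one sex and absent in the other. Divide λ = 10.37 by the variance of the difference between sexes relative to that of the overall treatment contrast, with df1 = 2 and df2 = (30 − 4) × 2 = 52. The overall contrast has variance proportional to 1/15 + 1/15 = 0.133.

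| Split | Variance of the sex difference | Ratio | λ | Power |
|---|---|---|---|---|
| 50-50 | 4/7.5 = 0.533 | 4.00 | 2.59 | 27% |
| 70/30 | 2/4.5 + 2/10.5 = 0.635 | 4.76 | 2.18 | 23% |
| 80/20 | 2/3 + 2/12 = 0.833 | 6.25 | 1.66 | 18% |

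**Step 5: how likely is 50-50?** If each completer is independently a woman with probability 0.30, the chance of 15 or more women among 30 is 1.7%. This is context only, since outreach may raise the share above the forecast.

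**The case against.** The best defence is that E7 is a recruitment section. It states an aspiration about outreach, and no test, subgroup or conclusion by sex is planned anywhere. That is correct, and it limits how much the point matters. It does not make the sentence true: the balance is aspirational, but the consequence drawn from it fails even if the balance is reached.

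Three stronger readings are tempting, and the documents do not support them.

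- A reader might infer that E1 and E7 contradict each other on the sex split. They do not. About 20% women is history, 70/30 is a forecast and 50-50 is a goal; E1 itself also promises efforts to recruit more women. The three can differ without conflict, although the protocol would be clearer if it labelled them.
- A reader might infer that the protocol promises by-sex analyses with 4 to 5 women per arm. E7 ties them to reaching 50-50, so 7 to 8 per sex per arm is the count on which the sentence should be judged. The lower counts show what the protocol itself leads one to expect.
- A reader might take the standardised difference of 0.6 under Measurements as the effect to be detected, in a single-visit comparison. That figure contrasts cocaine users with controls. It is neither a treatment effect nor part of the sample-size statement, and the planned model uses repeated visits. The power figures above therefore use the protocol's f = 0.24 and three visits.

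**Conclusion.** The capability claimed in E7 is not one the design has. At the 50-50 target, the planned effect would be detected within women 47% of the time, and a sex difference as large as the whole planned effect 27% of the time. At the forecast 70/30 split these fall to 27% and 23%. No split considered brings either sex subgroup, or the comparison between them, to 80%.

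The figures rest on 1:1 allocation, equal completion by sex, f read as 0.24, and three visits with correlation 0.5. The primary power statement reproduces on that basis and is unaffected, as are the three aims. This is a minor point about an overstated sentence, together with a balancing factor that the model omits; it is not a flaw in the main analysis.

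**What to change.** 1. In E7, replace the claim with a statement that sex-by-treatment estimates will be reported descriptively, with confidence intervals and without sex-specific conclusions. Keep the recruitment effort.
2. In E1 and E7, label 50-50 as the recruitment target and 70/30 as the expected split.
3. In Data Analyses, add gender as a covariate. Assignment is balanced on it, but the stated model has only suvorexant, time and their interaction. This is a change to the analysis as well as to the text.

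The cost is a less favourable stated capability and one model degree of freedom. No extra participants, visits or procedures are needed.
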